### **9.6 Device Accountability**

All use of the device will be under the direct supervision of the principal investigator or his/her designee. The investigational devices will be clearly labeled as investigational use only, and have a clearly marked serial number for each device, which clinical staff will record upon receipt of the device. The receipt date and serial number will be recorded, and package sterility confirmed. The devices will be individually stored in sterilized pouches and secured in the laboratory in the Lurie Biomedical Engineering Building at the University of Michigan North Campus until dispensed to the patient at Michigan Medicine Pediatric Otolaryngology Clinic.

All records of receipt, use, and disposition of the devices will be maintained by the study team. At the completion of the study, there will be a final reconciliation by study personnel of devices shipped, used, and devices remaining. Any discrepancies noted will be investigated, resolved, and documented prior to return or destruction of unused devices.

## **10.0 DATA ANALYSIS AND STATISTICAL CONSIDERATIONS**

### **10.1 Sample Size**

The sample size will be 5 pediatric patients with HUAO for the R61 phase and 40 pediatric patients for the R33 phase.

#### *10.1.1 Statistical power calculation for sample size (R33 phase):*

While we have demonstrated resolution of extremely severe OSA in our initial patients with hypotonia, the sample size calculation for the current trial is based on conservative assumptions. We defined a treatment response as meeting both a 50% reduction in AHI (e.g., 12.8 to 6.4) and post-treatment AHI<15 at Week 8. We considered this as the clinically meaningful improvement and designed the study to detect a difference in the proportion of children meeting clinically

meaningful improvement in OSA of 60% in the ssNPA device group vs. 18% in the SoC group. To detect a between-group difference of 60% vs. 18%, we will enroll 20 children per arm, for a total of 40 children, which will provide 80% power using a two-sided 0.05 level test. The study power will differ by the various assumptions. In particular, if the treatment response occurs in 15% or 20% of the ScC group enrollees, the proposed sample size will provide 75% and 86% power to detect the respective between-group differences in treatment response. We note that if a patient requires a tracheostomy within the 8 weeks of randomization, the patient will be considered not to have a treatment response. We expect further adjusting the primary analysis for baseline values of AHI will likely increase the power to detect the meaningful difference. For continuous outcomes such as PSQ or PedsQL, the proposed sample size is expected to give 80% power to detect an effect size of 0.89 SD or larger. We conservatively assume up to 20% dropout from the study where neither a tracheostomy nor a PSG is done, and to ensure that a total of 40 children have complete outcome data, we will enroll 50 children.

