### 9.4 R33 Phase – Randomization

After the R61 phase is successfully completed, for the R33 phase we will recruit 40 children with HUAO meeting the inclusion criteria of severe OSA (AHI>10 or >5 with hypoxemia) with the additional requirement that all subjects require the presence of at least one symptom of OSA (such as snoring 3 or more nights per week, daytime sleepiness, or hyperactive/inattentive behaviors). These latter symptoms will identify children at the highest risk for OSA and will minimize false positive from the baseline PSG. The exclusion criteria are the same as those delineated in the R61 phase clinical study.

Recruitment will occur from all clinics as well as community sources. In order to ensure that sufficient children complete the protocol and we have enough data from 40 subjects for our data analysis, we may recruit up to a total of 50 subjects to include for those children who may drop out before the end of 8 weeks study. All children will undergo a baseline PSG to determine eligibility and establish baseline data. All families will complete a questionnaire battery at the time of baseline PSG to acquire baseline measures. Eligible patients will be randomized 1:1 to receive (1) immediate therapy with the ssNPA device or (2) standard of care (SoC). The study will be designed as a randomized wait-list controlled clinical trial such that all children stand to benefit. Randomization will be stratified by baseline AHI scores (AHI>30 vs.  $\leq 30$ ).

At 8 weeks the ssNPA group will be able to continue the ssNPA for an additional 8 weeks while the SoC group will be offered the ssNPA for 8 weeks. At the end of the 8 week period, all children will undergo an in-laboratory PSG and repeat the questionnaire battery.

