## **10.2 Data Analysis**

### *10.2.1 R61 Phase:*

Analyses will be descriptive in the R61 phase of the study. The primary aim of the R61 phase is the 2nd generation ssNPA device confirmation and proof of concept that the ssNPA is tolerated and comfortable. For measures obtained using a 10-point scale including tolerability and comfort, we expect the margin of error for the mean estimate with 95% confidence to be 1.24 standard deviation. When tolerability and comfort measures are dichotomized (i.e., considering scores of 7 out of 10 as acceptable), the proposed sample size will give a margin of error of 0.19 for an estimate of proportion with positive responses.

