### *10.2.2 R33 Phase Statistical analysis:*

We will summarize subject characteristics by study arm. We will also summarize outcomes data at each assessment time and changes from baseline in outcome measures at each follow-up time by arm using appropriate summary measures including means, standard deviations, and proportions. If the data are highly skewed such as increasing variability with increasing mean, we will consider log-transformation. Primary outcomes will be treatment response at Week 8, defined as a clinically meaningful improvement in AHI of 50% reduction and AHI<15, and primary analytic cohort will be intent-to-treat. For the comparison of treatment response, receiving tracheostomy prior to Week 8 will be considered a treatment response failure. Although post treatment data are collected at Weeks 8 and 16, primary comparative analysis will be done using Week 8 data as the SoC group patients initiating the ssNPA at Week 8 will have self-selected to use the device and are not parallel to those initially randomized to the ssNPA. The between-arm difference in treatment response will be compared using a two-sample proportion test. Secondary outcomes will include various patient and caregiver outcome measures including AHI, PSQ, PedsQL and OSA-18. Improvement in each of these continuous measures will be compared between arms using mixed models with data at both baseline and Week 8 as the dependent variables, participants as random intercepts and an indicator for the ssNPA arm, an indicator for Week 8, and an interaction of Week 8 by ssNPA arm as the primary predictors. The parameter of the Week 8 by ssNPA arm interaction term will estimate the ssNPA effect. We will separately

report dropouts by arm and collect data on reasons for dropping out of the study. If dropout rate is more than 10%, for each outcome variable, we will perform an alternate parallel analysis where we will weigh the between-arm response comparisons inversely by the propensity of dropping out, with the propensities estimated separately from a logistic regression predicting dropout using baseline patient characteristics (e.g., age, sex, baseline AHI, treatment arm).

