### **10.4 Dropouts/Lost-to-Follow-up**

In order to achieve the 95% confidence and statistics specified above, we need a sample size of 5 patients. Thus, we will conservatively assume up to 20% dropout from the study, and to ensure that a total of 5 children have complete outcome data, we will enroll 7 children.

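### Two planning figures are wrong: R33 power at 15% and 20% standard-of-care response is transposed, and the R61 margin of error for a proportion with 5 children is about 0.43 at the 60% goal, not 0.19

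*Combined protocol and SAP*

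**What the plan says.** **R33 power (section 10.1.1).** The design target is "meaningful improvement in OSA of 60% in the ssNPA device group vs. 18% in the SoC group". On size and power, the plan states "we will enroll 20 children per arm, for a total of 40 children, which will provide 80% power using a two-sided 0.05 level test". The sensitivity statement follows: "if the treatment response occurs in 15% or 20% of the ScC group enrollees, the proposed sample size will provide 75% and 86% power", and the sentence ends "to detect the respective between-group differences in treatment response". The last phrase fixes the pairing as 75% power at 15% SoC response and 86% power at 20%. Allocation is 1:1 (section 9.4), and section 10.2.2 names the primary test: "The between-arm difference in treatment response will be compared using a two-sample proportion test".

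**R61 precision (sections 10.2.1 and 10.4).** For 5 children, section 10.2.1 gives a 95% margin of error of 1.24 SD for a mean. For tolerability and comfort scores that have been dichotomized, it says "the proposed sample size will give a margin of error of 0.19 for an estimate of proportion with positive responses". No assumed proportion is stated. Section 10.4 then says "In order to achieve the 95% confidence and statistics specified above, we need a sample size of 5 patients". The R61 goals reported by parents or observed in the child are each set at 60%, that is 3 of 5 (Table 3 in section 9.2; section 10.3.1).

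**The concern.** **Power.** The differences to detect are 45 points at 15% SoC response, 42 points at 18% and 40 points at 20%. As written, power goes from 75% to 80% to 86% while the effect shrinks. That is impossible at a fixed sample size with the ssNPA rate held at 60%. A SoC response above plan is the unfavourable case, and a reader such as a DSMB member is told that it strengthens the trial.

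**Margin of error.** A 95% margin of 0.19 on a proportion from 5 children is far tighter than 5 binary observations can normally give. If it is wrong, R61 is presented as locating the tolerability rate to within 19 points when it cannot, and section 10.4 uses that precision as part of its reason for 5 patients.

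**Working it through.** **Part (a): power**

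Inputs: 20 per arm, two-sided 0.05, ssNPA p1 = 0.60, SoC p2 = 0.18, 0.15 or 0.20 (all section 10.1.1); 1:1 allocation (section 9.4); two-sample proportion test (section 10.2.2).

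Pooled-variance normal approximation, with p̄ = (p1 + p2)/2:

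Power = Φ{ [√n·(p1 − p2) − 1.96·√(2p̄(1 − p̄))] / √(p1(1 − p1) + p2(1 − p2)) }

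1. Base case, p2 = 0.18, p̄ = 0.39: [4.472 × 0.42 − 1.96 × 0.6898] / 0.6226 = (1.878 − 1.352)/0.6226 = 0.845. Power is 80.1%. The plan's 80% is reproduced.
2. p2 = 0.15, p̄ = 0.375: (2.012 − 1.342)/0.6062 = 1.106. Power is 86.6%.
3. p2 = 0.20, p̄ = 0.40: (1.789 − 1.358)/0.6325 = 0.681. Power is 75.2%.

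| SoC response | Difference | Power stated | Power by the formula that gives the plan's 80% |
|---|---|---|---|
| 15% | 45 points | 75% | 86.6% |
| 18% | 42 points | 80% | 80.1% |
| 20% | 40 points | 86% | 75.2% |

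Other methods at 20 per arm do not rescue the stated order. Power at 15% and at 20%, in that order:

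- exact enumeration of the uncorrected chi-square test: 87.3% and 75.4%
- unpooled variance: 91.3% and 80.7%
- arcsine: 87.1% and 76.2%
- continuity-corrected: 77.0% and 62.9%
- Fisher's exact test: 79.7% and 65.0%
- one-sided: 92.8% and 84.8%
- difference held at 42 points instead of ssNPA at 60%: 81.5% and 79.4%

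Using the 25 per arm to be enrolled, before dropout, the pooled formula gives 93.3% and 84.5%. Every variant has more power at 15% than at 20%.

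**Part (b): margin of error**

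Inputs: n = 5 (section 10.1); 95% confidence (sections 10.2.1 and 10.4). The proportion is an assumption, because section 10.2.1 states none. I use 0.60, the R61 goal, and show a range.

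1. Mean: t(0.975, 4 df)/√5 = 1.242. The plan's 1.24 SD is reproduced, which confirms that n = 5 is the basis.
2. Proportion: 1.96·√(p(1 − p)/5). At p = 0.6, 1.96 × √0.048 = 0.429.

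| p | 0.5 | 0.6 | 0.7 | 0.8 | 0.9 | 0.95 |
|---|---|---|---|---|---|---|
| 95% margin, n = 5 | 0.438 | 0.429 | 0.402 | 0.351 | 0.263 | 0.191 |

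3. Sample size for a margin of 0.19 at p = 0.6: 1.96² × 0.24/0.19² = 25.5, so 26 children.
4. Small-sample intervals at 3 of 5 have half-widths of 0.33 (Wilson), 0.35 (Jeffreys) and 0.40 (Clopper-Pearson). The exact 95% interval is 0.15 to 0.95. For 4 of 5 it is 0.28 to 0.995.

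**The case against.** The strongest reply is that nothing in the design depends on either figure. The base case reproduces, and the sample size, enrolment, endpoint and primary test do not use the sensitivity sentence. Both power values are correct once exchanged. R61 is descriptive and its milestones are judged by counts, so the margin enters no test or go/no-go rule. Nor does R61 tolerability feed the R33 power calculation, where the 60% is AHI response. All of this stands, and it limits the remedy to text.

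On the margin, 0.19 is what the formula gives at p = 0.95, and 0.43 depends on taking p = 0.6. The condition should be stated. But the plan does not state p = 0.95, its goals are 60%, and 95% is not an observable result among 5 children. A Jeffreys interval at 0 of 5 or 5 of 5 also has a half-width of 0.19, but those results are equally far from the goal.

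Section 10.4 may also rest on the 1.24 SD, which is correct, so 0.19 is not the only support for 5 patients. It is still one of the statistics that section invokes.

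Whether SoC response will exceed 18% is open. The documents give no rate of spontaneous improvement, and section 9.4.2 considers PAP before the end of the trial unlikely. The transposition does not depend on that.

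**Conclusion.** Both figures are wrong as written.

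- **Power.** At 20% SoC response power is overstated by 10.8 points (86% stated, 75.2% computed). At 15% it is understated by 11.6 points (75% stated, 86.6% computed). This assumes ssNPA at 60% and 20 per arm with outcome data, as in section 10.1.1. The direction of the error holds under every method tried. A SoC rate only 2 points above plan takes power below the 80% target.
- **Margin of error.** The stated 0.19 is less than half of the 0.43 that applies at p = 0.6. It is too small for any true proportion between 0.5 and 0.9, and small-sample intervals at 3 of 5 are still about twice as wide. A result of 3 of 5 is compatible with true rates from 15% to 95%.

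The errors misstate the robustness of R33 and the precision of R61. They do not invalidate the R33 sample size.

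**What to change.** 1. Section 10.1.1: exchange the two values, so that a SoC response of 15% goes with about 86% power (86.6% by the pooled formula) and 20% with 75%. Name the formula used.
2. Section 10.2.1: replace 0.19 with a margin of about 0.43 at a true proportion of 60%, state that assumption, and add the exact 95% interval for 3 of 5 (15% to 95%).
3. Section 10.4: remove the claim that 5 patients are needed to reach that precision for a proportion. Describe 5 as a number chosen for feasibility, if that is the case; the 1.24 SD for a mean can stay.

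The cost is a text correction. Enrolment, endpoints and tests are unchanged. The stated R61 precision becomes less favourable, and R33 is shown to fall below 80% power if SoC response reaches 20%.

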## **10.2 Data Analysis**

### *10.2.1 R61 Phase:*

Analyses will be descriptive in the R61 phase of the study. The primary aim of the R61 phase is the 2nd generation ssNPA device confirmation and proof of concept that the ssNPA is tolerated and comfortable. For measures obtained using a 10-point scale including tolerability and comfort, we expect the margin of error for the mean estimate with 95% confidence to be 1.24 standard deviation. When tolerability and comfort measures are dichotomized (i.e., considering scores of 7 out of 10 as acceptable), the proposed sample size will give a margin of error of 0.19 for an estimate of proportion with positive responses.

### *10.2.2 R33 Phase Statistical analysis:*

We will summarize subject characteristics by study arm. We will also summarize outcomes data at each assessment time and changes from baseline in outcome measures at each follow-up time by arm using appropriate summary measures including means, standard deviations, and proportions. If the data are highly skewed such as increasing variability with increasing mean, we will consider log-transformation. Primary outcomes will be treatment response at Week 8, defined as a clinically meaningful improvement in AHI of 50% reduction and AHI<15, and primary analytic cohort will be intent-to-treat. For the comparison of treatment response, receiving tracheostomy prior to Week 8 will be considered a treatment response failure. Although post treatment data are collected at Weeks 8 and 16, primary comparative analysis will be done using Week 8 data as the SoC group patients initiating the ssNPA at Week 8 will have self-selected to use the device and are not parallel to those initially randomized to the ssNPA. The between-arm difference in treatment response will be compared using a two-sample proportion test. Secondary outcomes will include various patient and caregiver outcome measures including AHI, PSQ, PedsQL and OSA-18. Improvement in each of these continuous measures will be compared between arms using mixed models with data at both baseline and Week 8 as the dependent variables, participants as random intercepts and an indicator for the ssNPA arm, an indicator for Week 8, and an interaction of Week 8 by ssNPA arm as the primary predictors. The parameter of the Week 8 by ssNPA arm interaction term will estimate the ssNPA effect. We will separately

report dropouts by arm and collect data on reasons for dropping out of the study. If dropout rate is more than 10%, for each outcome variable, we will perform an alternate parallel analysis where we will weigh the between-arm response comparisons inversely by the propensity of dropping out, with the propensities estimated separately from a logistic regression predicting dropout using baseline patient characteristics (e.g., age, sex, baseline AHI, treatment arm).

In secondary analyses, we will use linear mixed models and fit longitudinally assessed outcomes data at baseline, Weeks 8 and 16 to assess the long-term effects of ssNPA. For binary treatment response, the outcomes assessed at Week 8 and 16 will be modeled using a generalized mixed model with logit link. The model will include participants as random intercepts and will include the ssNPA arm indicator, categorical time indicators for Weeks 8 and 16, and interactions of Week 8 by arm and Week 16 by arm. A significant interaction of Week 8 by ssNPA arm will provide evidence for ssNPA effect, and showing no difference in the coefficients between the two interaction terms of Week 8 by ssNPA arm and Week 16 by ssNPA arm will indicate NPA effect to remain long-term over the 4-month period. Prior to the longitudinal data modeling, we will graph cross-sectional means of outcome measures (e.g., percentage with treatment response) with SoC group stratified further to those that opted to receive ssNPA at Week 8 vs. not to visualize if their Weeks 8 and 16 data should be treated as a separate group or can be treated as additional data to ssNPA arm data. The data and model will allow us to explore for sub-hypotheses if the number of SoC group patients receiving ssNPA at Week 8 is substantial. We note, however, that the Week 16 outcomes of SoC group patients will be interpreted carefully as they reflect outcomes in participants who opt to use or not use ssNPA after having been exposed to the standard care under a research setting for an 8-week period.

Of critical importance will be subgroup of patients who have OSA severity with AHI>30. These Patients with HUAO and extremely severe OSA are likely to fail surgical interventions other than tracheostomy and as such will be considered “warranting tracheostomy”. Given the proposed sample size and the known prevalence of about 20% of hypotonic patients with severe apnea, we expect a total of about 8-10 patients “warranting tracheostomy”. We will report, by each arm, the number (%) receiving tracheostomy in all study enrollees and in those with baseline AHI>30 by Week 8. We will also report the number (%) receiving tracheostomy in those randomized to ssNPA arm by Week 16. These data will be used for future power calculations to determine sample size requirements for larger trials focused on the utility of the ssNPA in tracheostomy avoidance.

Another important parameter is adherence, which will be reported as percentage of participants using the device at two months after initiation in both the active group (ssNPA) and in the wait list group (SoC) participants who received the device at Month 2. In the active group, we will compare adherence rates between treatment responders (those with >50% reduction in AHI and AHI<15 at Week 8) and non-responders to assess the relationship between adherence and treatment response. However, since clinically meaningful improvement can be accomplished by using ssNPA without the need for continued use of the device for two months, we will carefully analyze the daily

adherence data obtained using diaries to have a better understanding of the relationship between adherence during the first 8 weeks and treatment response.

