Families will return to the clinic at weeks 2 and 4 to ensure optimal care and evaluate the device safety, tolerability, and acceptability. In between the clinic visits, regular contact will be made with families by the team, daily during the first week and weekly by the 2nd week (see Appendices H-K). During these calls, caregivers will report night to night witnessed apneas, improvement in daytime awareness, improvement in sleeping patterns of the patient, and any adverse events. Beside the two clinical visits at 2nd and 4th week, the number and frequency of extra visits will depend on: (1) the child's current threshold; and (2) how the child and family advance through each step of the desensitization protocol. The decision to hold on a particular step of the desensitization program will be based on whether the child's current level of anxiety or opposition is elevated. A recommendation to discontinue ssNPA treatment may be made if the child or family do not make progress with wearing the device in 2-4 weeks (depending on the number of visits during that time). Discontinuation of ssNPA therapy may occur after case consultation with other members of the study team to ensure that all strategies have been considered.

Evaluation of the device safety, tolerability, and acceptability will be assessed by a survey of patients and caregivers using a validated questionnaire with 10-point response scale (Appendix K). Mean and standard deviation scores as well as the percentage of those reporting satisfactory or better will be assessed. Device safety will be determined by adverse events

Table 3. Milestones for successful completion of the R61 phase

R61 Milestones	Goal (out of 5 subjects)
1. Device optimization and manufacturing in clean/sterile manner	100%
2. Parent report of ease of insertion; $\geq 5$ on Likert scale of 1-10	60% (3 of 5)
3. Child able to tolerate device in place	60% (3 of 5)
4. Child able to maintain device in place during sleep	60% (3 of 5)
5. Parent report of adherence based on diary	60% (3 of 5)
6. Comfort rating $\geq 6$ on Likert scale of 1-10	60% (3 of 5)

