### **Stage 3: In lab sleep study**

When the patient has fully acclimated to the device, at approximately 8 weeks, an in-lab PSG will be performed in the UM Sleep Disorders Laboratory in order to quantify the relief of obstruction (measured by AHI) while wearing the ssNPA. Sleep studies will include six EEG channels (F3-A2, F4-A1, C3-A2, C4-A1, O1-A2, O2-A1 of the 10-20 international electrode placement system), 2 electro-oculogram channels (right and left outer canthi), chin and bilateral anterior tibialis surface EMG, 2 EKG leads, nasal and oral airflow (thermocouples), nasal pressure through pediatric sensor cannulae, thoracic and abdominal excursion (inductance plethysmography), and finger oximetry with pulse waveform. All recordings will be made on digital equipment (Compumedics, Inc.) with which the investigators have extensive laboratory-wide clinical and research experience. End-tidal or transcutaneous CO2 will be monitored per the AASM guidelines for pediatric PSG [22]. A research coordinator and a physician will be on call by page during the studies. Nocturnal PSGs will be scored by a single, experienced technologist masked to subject identity. Borderline polysomnographic features will be arbitrated between the technician and [name], MD, pediatric sleep physician. Scoring for sleep stages, respiratory events, periodic leg movements, and arousals will follow standard criteria for children [22].

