## **9.5 TREATMENT INTERRUPTIONS-DISCONTINUATION CRITERIA**

### ***9.5.1 Treatment Interruption Criteria***

In the event of patient illness, the patient will temporarily stop study treatment. Because nasal secretions and other upper respiratory symptoms can interfere with accurate data measurement and observation of treatment, the patient will have the option of pausing using the device until symptoms subside. Alternatively, if caregivers feel the device is providing symptomatic relief during the concurrent illness, they may continue use – however assessments, such as PSG will be postponed until resolution of acute illness to minimize artifact. Additionally, in the event of any temporary family emergency or necessary situation, the patient may also temporarily stop using the device. If for some reason there is a need for a different sized device, the treatment maybe paused while the new device is manufactured and delivered to the family. Observation will resume once the patient is treated with the new device.

The decision to hold on a particular step of the desensitization program will be based on whether the child's current level of anxiety or opposition is elevated. A recommendation to discontinue ssNPA treatment may be made if the child or family do not make progress with wearing the device in 2-4 weeks (depending on the number of visits during that time). Discontinuation of ssNPA therapy may occur after case consultation with other members of the study team to ensure that all strategies have been considered.

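### The R33 primary analysis is labelled intent-to-treat but has no rule for a randomised child with neither a tracheostomy nor a Week 8 PSG, and the stated 80% power counts only children with outcome data

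*Combined protocol and SAP*

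**What the plan says.** Response is defined in section 10.1.1: "We defined a treatment response as meeting both a 50% reduction in AHI (e.g., 12.8 to 6.4) and post-treatment AHI<15 at Week 8". Section 10.2.2 compares response between arms with a two-sample proportion test and states that the "primary analytic cohort will be intent-to-treat". Both sections count tracheostomy before Week 8 as non-response. No other reason for a missing outcome has a rule.

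The sample size is given as "To detect a between-group difference of 60% vs. 18%, we will enroll 20 children per arm, for a total of 40 children". The power claimed for that number is 80% at a two-sided 5% level. Section 10.1.1 then assumes up to 20% dropout, meaning children with neither a tracheostomy nor a PSG, and continues: "to ensure that a total of 40 children have complete outcome data, we will enroll 50 children". Section 9.4 likewise refers to having data from 40 subjects for the analysis.

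If dropout exceeds 10%, section 10.2.2 adds a parallel analysis weighted by the inverse propensity of dropping out. The propensities come from baseline characteristics, with age, sex, baseline AHI and arm as examples. Dropouts and their reasons will be reported by arm.

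On stopping the device, section 9.2 (Stage 2) says: "A recommendation to discontinue ssNPA treatment may be made if the child or family do not make progress with wearing the device". Section 9.5.1 repeats this. Neither section says whether the Week 8 PSG still takes place. Section 10.3.3 expects the device to be tolerated by more than 60% of children and parents.

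**The concern.** An intent-to-treat label promises an answer for every randomised child. Here up to one in five is expected to have no Week 8 PSG and no tracheostomy, and the plan does not say what happens to them in the primary test. Three features make an observed-case comparison the most natural reading: the power counts children with outcome data, enrolment is inflated to reach that number, and dropout is handled only in an alternative analysis.

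This matters because one reason for leaving exists only in the ssNPA arm during the first 8 weeks, namely failure to tolerate the device. If such children leave without a PSG, they drop out of the ssNPA denominator, and they are likely non-responders. The planned weighting would be triggered at the plan's own 20% dropout, but it uses only information known at baseline. Intolerance shows itself afterwards. If the weighted and unweighted results disagree, the treatment of missing outcomes could be settled after the data have been seen.

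**Working it through.** **Inputs.** Response 60% vs 18%, two-sided 0.05, 20 per arm with outcome data, 20% dropout and 50 enrolled (section 10.1.1); 1:1 allocation (section 9.4), so 25 per arm randomised; two-sample proportion test (section 10.2.2). Dropout by arm is not given, so every split below is an assumption.

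**1. The plan's own figures.** With p̄ the mean of the two rates,

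power = Φ{ [ |p1 − p2| − 1.96·√(2p̄(1 − p̄)/n) ] / √([p1(1 − p1) + p2(1 − p2)]/n) }.

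For n = 20 and p̄ = 0.39: (0.42 − 1.96 × 0.1542)/0.1392 = 0.845, so power is 80.1%. Exact enumeration of the pooled z-test gives 80.5%. Enrolment is 40/(1 − 0.20) = 50. Both stated figures reproduce, and both rest on children with an outcome.

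**2. How far an observed-case rate can be off.** If the all-randomised ssNPA rate is r, a fraction d leaves without a PSG, and all who leave are non-responders, the observed rate is r/(1 − d).
- d = 20%: 48%/0.80 = 60%.
- d = 40%: 36%/0.60 = 60%.

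A worked case puts all 10 planned dropouts in the ssNPA arm.
- Observed cases: 9/15 (60%) vs 5/25 (20%). Pooled rate 0.35, SE 0.156, z = 2.57, p = 0.010.
- All randomised: 9/25 (36%) vs 5/25 (20%). Pooled rate 0.28, SE 0.127, z = 1.26, p = 0.21.

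**3. False-positive rate.** Suppose the all-randomised response is 18% in both arms and only ssNPA non-responders are lost. The exact two-sided rejection rate of the observed-case pooled z-test is:
- no loss (25 vs 25): 5.5%;
- 20% ssNPA loss (20 children at 22.5% vs 25 at 18%): 6.6%;
- 40% ssNPA loss (15 children at 30% vs 25 at 18%): 17.2%.

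**4. Power with all 25 per arm analysed and missing counted as non-response.** The first three rows take 60%/18% as rates among observed children and multiply by (1 − dropout).

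| Assumed dropout, ssNPA / SoC | Rates, all randomised | Difference | Power, formula | Power, exact |
|---|---|---|---|---|
| 20% / 20% | 48.0% vs 14.4% | 33.6 points | 74.2% | 76.4% |
| 8/25 / 2/25 | 40.8% vs 16.6% | 24.2 points | 47.3% | 49.5% |
| 10/25 / 0/25 | 36.0% vs 18.0% | 18.0 points | 29.5% | 31.1% |
| 60%/18% already apply to all randomised | 60% vs 18% | 42 points | 88.5% | 90.1% |

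First row by formula: p̄ = 0.312, (0.336 − 1.96 × 0.1310)/0.1221 = 0.648, Φ = 0.742. Rows two and three both have 20% dropout overall, and in both an observed-case analysis would still show 42 points.

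**5. The opposite direction.** Counting missing as non-response is not always conservative. With 18% response in both arms, random dropout, and 2/25 ssNPA vs 8/25 SoC missing, the rates become 18% × 0.92 = 16.6% and 18% × 0.68 = 12.2%, a spurious advantage for the device.

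**The case against.** The strongest reply is that the plan says intent-to-treat and nowhere excludes a child without a PSG. Raising 40 to 50 is a sample-size step and does not define an analysis set. That is correct: a reader might infer that the primary test is a completers' analysis, but the text leaves this open. What stands is that no rule puts these children into the test.

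Second, stopping the device is not leaving the study. Section 9.5.2 treats study withdrawal separately, and section 9.4 plans a PSG for all children. Section 10.2.2 compares adherence between ssNPA responders and non-responders, which suggests that poorly adherent children are expected to have Week 8 outcomes. A child who stops but attends the PSG stays in the denominator. This stands, and it makes the bias conditional.

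Third, a reader might infer that the ssNPA PSG waits for acclimation while the SoC PSG runs on a fixed clock. Stage 3 does say "When the patient has fully acclimated to the device, at approximately 8 weeks, an in-lab PSG will be performed", but section 9.2 reads mainly as the R61 procedure. Sections 9.4.1, 9.4.2 and 11.8.2 put the R33 PSG at 8 weeks in both arms. The section 9.5.1 sentence "Observation will resume once the patient is treated with the new device" concerns replacing a wrongly sized device, and the same section postpones the PSG during acute illness to limit artefact. These passages need reconciling, but they do not establish a timing difference between arms.

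Fourth, the assumed splits are illustrative. SoC families are telephoned specifically to limit dropout, but SoC losses could still be the larger. As step 5 shows, missing-as-failure could then favour the device, which is why sensitivity analyses are part of the remedy.

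**Conclusion.** The point holds as a gap in the definition of the primary analysis. The cohort is called intent-to-treat, the power rests on children with outcome data, and a child with neither a tracheostomy nor a Week 8 PSG has no defined place in the test. The parallel weighting does not close the gap, because device intolerance is not a baseline characteristic.

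The documents do not support the stronger statement that the result is biased toward the device. Overstatement requires losses that are larger in the ssNPA arm, or more concentrated there among non-responders. The documents give neither dropout by arm nor response among those lost. Under the assumptions shown, the choice of denominator can move p from 0.010 to 0.21, and the false-positive rate can reach 6.6% to 17.2%.

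Power on all randomised children is about 74–76% with equal 20% dropout, about 50% with an 8/25 vs 2/25 split, and about 88–90% if 60%/18% already describe all randomised children. An open choice in the primary endpoint that could change the conclusion should be closed before any outcome data are seen.

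**What to change.** - Define the primary set as all randomised children (about 50), analysed as randomised.
- Count a missing Week 8 PSG as non-response, extending the existing tracheostomy rule.
- Pre-specify an observed-case analysis and a tipping-point (or multiple-imputation) analysis as sensitivity analyses. Keep the weighted analysis as supportive, and say that it adjusts for baseline factors only.
- State that children who stop the device remain in follow-up and are asked to have the Week 8 PSG, and state under what condition (device in place or not) it is recorded.
- Time that PSG from randomisation in both arms, as sections 9.4.2 and 11.8.2 already say. Reconcile this with the acclimation wording in section 9.2 (Stage 3) and with the pause and acute-illness provisions in section 9.5.1.
- Say whether 60%/18% refer to observed or to all randomised children, and restate power for 25 per arm over a stated range of dropout by arm.

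**Cost.** This changes analysis and protocol wording and needs no extra patients. The stated power may become less favourable. If 60%/18% apply to observed children with equal 20% dropout, keeping 80% would take 29 per arm by the formula, so the sponsor would either accept about 74–76% or decide on a larger trial openly.
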